### 8.2 SAMPLE SIZE DETERMINATION

A power analysis was conducted at 0.8 with an alpha of 0.05, using liposomal bupivacaine and ISC complication rates calculated from prior literature.

### 8.3 STATISTICAL ANALYSES

Data analysis was performed using IBM SPSS Statistics for Macintosh, version 27 (IBM Corp., Armonk, NY, USA). Prior to study arm comparison, a Shapiro-Wilk test was performed, which indicated non-normally distributed data.

Patient age, BMI, operative time, perioperative pain scores, medication consumption, duration and quality of sleep, satisfaction, and preoperative and postoperative PROMs (VAS, SANE, ASES, and PSS) were compared using Mann-Whitney U tests.

Additional patient demographics, including gender, smokable tobacco consumption, intraoperative complications, ASA classification, CCI scores, surgical procedures, and 6 perioperative complications (nausea, dyspnea, anesthetic site discomfort and/or irritation and/or leakage, and self-reported complications), were compared with chi-squared tests. Graded measures, such as anesthetic site discomfort and irritation, were dichotomized based on severity, into “none-to-mild” and “moderate-to-severe” categories for analysis. Statistical significance was set to  $P < .05$ .

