## 1 PROTOCOL SUMMARY

### 1.1 SYNOPSIS

Title:	Nerve block with liposomal bupivacaine yields fewer complications and similar pain relief when compared to an interscalene catheter for arthroscopic shoulder surgery: a randomized controlled trial
Study Description:	This is a blinded, randomized controlled trial to compare the control arm (continuous ropivacaine ISC) to the experimental arm (single-injection, brachial plexus nerve block using liposomal bupivacaine) in patients undergoing outpatient arthroscopic shoulder surgery at a single, tertiary academic institution.
Objectives:	

• Compare complication rates

• Compare pain level, dose frequency of prescribed opioid analgesics, consumption of prescribed nonopioid analgesics, quantity and quality of sleep, and overall satisfaction with pain control

• Compare patient-reported outcome measures

Endpoints:	

• Patient reported complications on post-op day 0, 1, 2, 3, and 4

• Visual Analog Scale, prescribed opioid analgesic dose frequency, consumption of prescribed nonopioid analgesics, hours of uninterrupted sleep, subjective quality of sleep (0-10 scale), and pain control overall satisfaction (five-point Likert scale) on post-op day 0, 1, 2, 3, and 4

• Visual Analog Scale, Single Assessment Numeric Evaluation, American Shoulder and Elbow Surgeons Standardized Shoulder Assessment Form, and Penn Shoulder Score at 12 weeks post-op

Study Population:	Patients greater than 19 years of age undergoing outpatient arthroscopic shoulder surgery
Phase:	Not Applicable

Description of Study Intervention:	Patients in the ISC arm will have a 19 gauge Arrow Continuous Nerve Catheter (Teleflex, Wayne, PA, USA) placed with a bolus of 15-20 mL of 0.5% ropivacaine given through the needle prior to threading the catheter. An elastomeric, basal-only, On-Q infusion pump (Avanos Medical, Alpharetta, GA, USA) with 0.2% ropivacaine will be started in the post-anesthesia care unit at 8 mL/hour, and the catheter will be removed by the patient after two days. For patients in the LB arm, 10 mL (133 mg) of liposomal bupivacaine (Pacira BioSciences, Parsippany, NJ, USA) mixed with 7 mL (35 mg) bolus of 0.5% bupivacaine will be injected.
Study Duration:	January 1, 2020 to December 1, 2021
Subject Duration:	3 months

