## 3 STUDY DESIGN

### 3.1 OVERALL DESIGN

Patients undergoing arthroscopic shoulder surgery were prospectively assessed after randomization into either ropivacaine ISC or single-injection liposomal bupivacaine brachial plexus nerve block (LB) arms. All patients were

discharged with 5 analgesics (acetaminophen, methocarbamol, gabapentin, acetylsalicylic acid, and oxycodone) for as-needed pain relief. Preoperatively, patient demographics and baseline Visual Analog Scale, Single Assessment Numeric Evaluation, American Shoulder and Elbow Surgeons, and Penn Shoulder Scores were obtained. For the first four days postoperatively, complication rates (nausea, dyspnea, anesthetic site discomfort and/or irritation and/or leakage, and self-reported concerns and complications), pain, medication usage, and sleep data were assessed by phone survey every 12 hours. The primary outcome was overall complication rate. At 12 weeks postoperatively, Visual Analog Scale, Single Assessment Numeric Evaluation, American Shoulder and Elbow Surgeons, and Penn scores were reassessed. Outcome scores were compared with Mann-Whitney U tests, and demographics were compared with chi-squared tests. Significance was set at  $P < .05$ .

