## 8 STATISTICAL CONSIDERATIONS

### 8.1 STATISTICAL HYPOTHESES

- Primary Efficacy Endpoint(s): Postoperative Pain Scores
- Secondary Efficacy Endpoint(s): Postoperative Oral Morphine Equivalents, Analgesia Satisfaction, Analgesia Complications, Sleep Quality, and Hours of Painless Sleep

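### Section 8.3 compares repeated early outcomes, including pain (primary in 8.1), only by unadjusted Mann-Whitney tests and never says which value per patient is tested

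*Combined protocol and SAP*

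**What the plan says.** Section 1.2 schedules nine calls: the evening of day 0, then morning and evening on days 1 to 4 (1 + 4 × 2 = 9). Section 3.1 confirms the frequency: "pain, medication usage, and sleep data were assessed by phone survey every 12 hours". Section 7.1 asks about medication, pain and sleep at each call. The synopsis (1.1) lists the early outcomes by day, ending with "pain control overall satisfaction (five-point Likert scale) on post-op day 0, 1, 2, 3, and 4".

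Section 8.1 gives "Primary Efficacy Endpoint(s): Postoperative Pain Scores", with no time point and no summary measure. For the repeated outcomes, listed as "perioperative pain scores, medication consumption, duration and quality of sleep, satisfaction", 8.3 says only that they "were compared using Mann-Whitney U tests", and then: "Statistical significance was set to" P < .05. No section defines a value per patient, a primary time point, a model for repeated values, a testing order or an adjustment. ANCOVA and least-squares means appear in the abbreviation list but nowhere in the analysis.

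Two other sections bear on how much this matters. Section 3.1 names the overall complication rate as the primary outcome. Section 8.2 says "A power analysis was conducted at 0.8 with an alpha of 0.05", "using liposomal bupivacaine and ISC complication rates calculated from prior literature".

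**The concern.** A Mann-Whitney test takes one independent value per patient. Here each patient supplies several values, and the plan does not say how they become one. An analyst who follows the synopsis day by day runs five tests per outcome. One who follows the call schedule runs nine for pain and medication. Each test is at .05, and nothing says which of them decides the question.

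Two things are at stake. First, the 5% level does not hold for an outcome if any one of several time points can be reported as a difference. Second, pain has no single comparison. The trial's title anticipates similar pain relief, and 2.3.2 speaks of superiority or non-inferiority. Either needs one estimated difference with a confidence interval, and a set of time-point P values does not supply it.

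**Working it through.** The plan states no error rate for these outcomes, so there is no figure to reproduce.

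**Inputs from the documents.** Five days (1.1), nine calls (1.2), the Mann-Whitney test and a threshold of .05 (8.3).

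**Assumed inputs.** Within-patient correlation between times of 0.3, 0.5 and 0.7, equal for all pairs; 35 patients per arm (also 20 and 60); two-sided tests. The documents give none of these.

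**Step 1: upper reference, independent tests.** 1 − 0.95^5 = 22.6% for five times; 1 − 0.95^9 = 37.0% for nine. Repeated values from one patient are correlated, so the true figures are lower.

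**Step 2: correlated tests with no true difference.** Two methods were used: correlated normal test statistics (400,000 draws), and actual Mann-Whitney tests on rounded 0-10 scores (4,000 simulated trials per case).

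| Chance of a false P < .05 | corr. 0.3 | corr. 0.5 | corr. 0.7 |
|---|---|---|---|
| Any of 5 daily tests, normal statistics | 20.9% | 18.4% | 14.8% |
| Any of 5 daily tests, Mann-Whitney | 21.4% | 18.0% | 15.2% |
| Any of 9 call tests, normal statistics | 32.6% | 26.8% | 20.3% |
| Any of 9 call tests, Mann-Whitney | 32.3% | 28.2% | 20.5% |
| One test on the 9-call mean, Mann-Whitney | 4.7% | 5.3% | 4.6% |

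The missing sample size matters little. For nine times at correlation 0.5, the any-test figure is 26.6% with 20 per arm and 28.3% with 60.

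**Step 3: pooling nine calls as if from different patients.** Type I error is approximately 2 × [1 − Φ(1.96 / √(1 + 8ρ))].
- ρ = 0.3: √3.4 = 1.844, giving 28.8%.
- ρ = 0.5: √5 = 2.236, giving 38.1%.
- ρ = 0.7: √6.6 = 2.569, giving 44.6%.

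Mann-Whitney simulation gives 28.1%, 38.0% and 42.5%, so the range over both methods is about 28-45%.

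**Step 4: precision of a summary.** The variance of a nine-call mean relative to one call is (1 + 8ρ)/9: 0.38, 0.56 and 0.73 at ρ = 0.3, 0.5 and 0.7. A difference sustained over the calls is therefore easier to detect with the mean than at any single call.

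**Step 5: how many values each outcome has.**
- Pain and medication: up to nine.
- Sleep: 7.1 asks about the previous night. Morning and evening calls on one day refer to the same night, and the day 0 call refers to the night before surgery. About four distinct postoperative nights remain.
- Satisfaction: listed by day in 1.1, but not an item in the 7.1 call survey.

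**The case against.** The strongest reply is that 8.3 is silent, and silence is not an instruction to test every time point. One Mann-Whitney test on a per-patient total or mean fits its wording and would hold 5%. For medication, recorded as pills since the previous call, a total is the natural choice. This stands: inflation is left open, not dictated. The day-by-day endpoint list still makes per-day testing the most literal reading.

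A reader might infer that calls will be pooled as independent observations. No section says so. The text merely fails to exclude it, so the 28-45% describes a possible misuse and not the plan.

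A reader might also take all six outcomes as having nine values each. Step 5 of the working shows that this fails for sleep and satisfaction.

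A third reply is that complications may be the real primary outcome: 3.1 says so and 8.2 bases the power on them. This also stands. The documents do not support saying that the trial's main conclusion lacks a valid test; they support it only for the primary endpoint that 8.1 names.

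Finally, spurious pain differences would work against a claim of similar pain relief, so the error does not simply favour the new treatment. That is fair, but a similarity claim still needs one defined comparison, and there is none.

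**Conclusion.** The point holds in a limited form. For outcomes recorded repeatedly, 8.3 specifies a test but not the value tested, and has no rule for multiplicity. Read literally, for pain this means about a 15-21% chance of at least one false positive over five daily tests, or 20-33% over nine calls, against a nominal 5%. These ranges rest on assumed correlations of 0.7 down to 0.3. The direction does not depend on them unless repeated values are almost perfectly correlated.

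The weight depends on a contradiction that the documents must resolve. If pain is primary (8.1), this must be fixed, because the primary endpoint has no defined test. If the complication rate is primary (3.1, 8.2), it concerns a secondary outcome and should be fixed.

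**What to change.** Reconcile 3.1, 8.1 and 8.2 on the primary endpoint. Then, in 8.3, define one value per patient and one test per outcome:

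- **Pain:** the mean over the postoperative calls, or a longitudinal model with a patient effect and one pre-specified contrast.
- **Opioids:** one cumulative total.
- **Nonopioid analgesics:** likewise one value per patient.
- **Sleep duration and quality:** one mean each over distinct postoperative nights.
- **Satisfaction:** one per-patient mean of the daily ratings, stating where these are collected.

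Report each arm difference with a confidence interval. Show per-day and per-call results descriptively, without significance claims. Label secondary outcomes as exploratory or adjust across them: six single tests at .05 still carry up to 1 − 0.95^6 = 26.5% if independent. State that calls are never pooled as independent observations.

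Section 8.3 is in the past tense and already reports a Shapiro-Wilk result. It should therefore say whether the summary was chosen before or after the data were seen; if after, the result should be labelled so.

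The cost is mainly wording, and pain, medication and sleep need no new data. The downsides are that a difference confined to one call or day may be missed, and that single-day P values lose confirmatory status.

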## 7 STUDY ASSESSMENTS AND PROCEDURES

## 7.1 STUDY ASSESSMENTS

- twice-daily phone calls for the first 4 days post-surgery

At each phone call, the following surveys will be performed:

- Medication Intake Survey
  - Since the last phone call:
    - Which medications have been consumed?
    - How many pills?
- Pain Survey
  - On a scale of 1-10, with 10 being the worst, what is your pain right now?
- Sleep Quality Survey
  - On a scale of 0-5, with 5 being the best, how was your sleep last night?
  - How many hours were you able to sleep before being interrupted by pain?

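### Early (Days 0-4) pain is compared without adjustment for the preoperative VAS already collected; the test is valid, but some precision may be lost, of a size the documents do not allow to be fixed

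*Combined protocol and SAP*

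**What the plan says.** Section 8.1 lists "Primary Efficacy Endpoint(s): Postoperative Pain Scores", with no time point. Section 3.1 says instead "The primary outcome was overall complication rate", and section 8.2 describes power of 0.8 at an alpha of 0.05 based on complication rates.

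The early window comes from other places. Section 3.1 says that over the first four days "pain, medication usage, and sleep data were assessed by phone survey every 12 hours"; the schedule in 1.2 lists nine calls from the evening of Day 0 to the evening of Day 4; and the item in 7.1 reads "On a scale of 1-10, with 10 being the worst, what is your pain right now". The synopsis calls the early pain measure a VAS and also lists VAS at 12 weeks.

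On baseline, section 3.1 says "Preoperatively, patient demographics and baseline Visual Analog Scale, Single Assessment Numeric Evaluation, American Shoulder and Elbow Surgeons, and Penn Shoulder Scores were obtained", with no restriction to a subgroup.

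On analysis, section 8.3 puts early pain in one list with the other scores: "perioperative pain scores, medication consumption, duration and quality of sleep, satisfaction, and preoperative and postoperative PROMs (VAS, SANE, ASES, and PSS) were compared using Mann-Whitney". I read its perioperative pain scores as the phone-call scores. No adjusted, stratified or repeated-measures analysis of pain is described. ANCOVA and LSMEANS appear only among the abbreviations in 9.2. Section 8.3 mentions a Shapiro-Wilk result showing non-normality, but gives no reason for leaving the baseline out.

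**The concern.** Preoperative VAS is a baseline measure of the same construct as the early-pain outcome. If the two are correlated, the part of the outcome's variance that baseline explains stays in the error term of an unadjusted comparison, and power to detect an arm difference in pain is lower than the collected data would allow. Comparing preoperative VAS between arms does not recover that precision and does not correct a chance imbalance.

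Pain matters to the trial's message whatever its formal rank. The title speaks of similar pain relief, and the power calculation does not cover pain. Section 8.3 sets only a significance threshold, so a reader of the pain result is not promised an estimate with an interval.

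Non-normality does not force the choice. Rank ANCOVA, a proportional-odds model, or ANCOVA with robust or bootstrap standard errors can all take a baseline covariate.

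**Working it through.** **Is there a figure to reproduce?** No. Section 8.2 gives power 0.80 and alpha 0.05 for complication rates, but not the rates or the resulting N. No SD, effect size, power or rho is given for pain. What follows is therefore a range under stated assumptions: two-sided alpha 0.05, 1:1 allocation, and 80% power for the unadjusted pain comparison. The 80% is borrowed from 8.2, which does not apply it to pain.

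**Formula.** Adjusting for a baseline with correlation rho to the outcome multiplies the residual variance by (1 - rho²). At 80% power the unadjusted signal is 1.960 + 0.842 = 2.802 standard errors, so

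power after adjustment = Φ[2.802 / √(1 - rho²) - 1.960].

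| rho (assumed) | 1 - rho² | 2.802 / √(1 - rho²) | Power | Gain (points) |
|---|---|---|---|---|
| 0 | 1.00 | 2.802 | 0.800 | 0 |
| 0.1 | 0.99 | 2.816 | 0.804 | 0.4 |
| 0.2 | 0.96 | 2.860 | 0.816 | 1.6 |
| 0.3 | 0.91 | 2.937 | 0.836 | 3.6 |
| 0.4 | 0.84 | 3.057 | 0.864 | 6.4 |
| 0.5 | 0.75 | 3.235 | 0.899 | 9.9 |

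A gain of 5 points needs rho of about 0.36 (power 0.852).

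**The same in patients.** At an assumed standardised difference of 0.5, the unadjusted comparison needs 63 per arm for 80% power. Multiplying by (1 - rho²) and rounding up gives 61 (rho 0.2), 58 (0.3), 53 (0.4) and 48 (0.5).

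**Check with rounded, bounded scores.** The formula is for normal data, so Mann-Whitney was compared with rank ANCOVA in simulations. Sample sizes are assumed. Entries are power, Mann-Whitney / rank ANCOVA.

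| rho | A: 40 per arm | B: 35 per arm | C: 40 per arm | D: 40 per arm, half of controls at the scale floor |
|---|---|---|---|---|
| 0 | 0.805 / 0.800 | 0.816 / 0.812 | 0.798 / 0.793 | - |
| 0.1 | - | - | 0.806 / 0.804 | 0.841 / 0.838 |
| 0.15 | - | 0.800 / 0.808 | - | - |
| 0.2 | 0.796 / 0.815 | - | 0.810 / 0.824 | 0.842 / 0.847 |
| 0.3 | 0.798 / 0.827 | 0.825 / 0.857 | 0.798 / 0.822 | 0.831 / 0.854 |
| 0.4 | 0.796 / 0.854 | - | - | - |
| 0.5 | 0.805 / 0.887 | 0.825 / 0.898 | - | - |

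The simulated gains are 0.5 to 1.9 points at rho 0.2, 2.3 to 3.2 at 0.3, 5.8 at 0.4, and 7.3 to 8.2 at 0.5. At rho 0 to 0.1 the adjusted test is lower by 0.2 to 0.5 points, which is negligible. Under no arm difference, rejection rates in A and B stayed at about 4% to 6% for both tests.

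Formula and simulation together give about 1-2 points at rho 0.2, 2-4 at 0.3, 6 at 0.4, and 7-10 at 0.5. The proportional-odds model was not simulated.

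**The case against.** **The benefit may be very small.** Nothing in the documents supports a particular rho. Early pain is rated under a nerve block, and the synopsis keeps the catheter in for two days, so the link with preoperative pain could be weak. This stands: below rho of about 0.2 the gain is negligible, and a gain of 5 points needs about 0.36.

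**Pain may not be primary.** If section 3.1 governs, this is an efficiency point on a secondary outcome. That also stands. It lowers the priority but does not change what 8.3 does with the baseline.

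**Changing the main analysis now is post hoc.** Section 8.3 is written in the past tense and already reports a Shapiro-Wilk result. Replacing the stated test with an adjusted one after arm results are known would be a concern in itself. This stands and shapes the fix.

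**Stronger readings that the documents do not support.** A reader might infer that the unadjusted comparison is biased or has an inflated error rate. It does not: under randomisation it is valid. A reader might infer that ignoring chance imbalance in preoperative pain favours a non-significant result. Imbalance can push either way, and its average effect is already in the unadjusted test's variance, so counting it as well as the lost precision counts it twice. A reader might also infer that adjustment would justify a claim of similar pain relief. It would not: no non-inferiority margin for pain is stated, and that is a separate problem.

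**Conclusion.** The point holds as a matter of efficiency. Section 8.3 leaves a collected baseline measure of pain out of the early-pain comparison and gives no reason. The direction of the loss is confirmed by the formula and by simulation once rho is about 0.2 or more. Its size for this trial is unknown: it runs from essentially nothing to about 10 points of power over rho from 0.1 to 0.5, and every figure rests on an assumed rho and an assumed 80% starting power. The point concerns the phone-call pain scores, not the 12-week scores. It does not show that the pain result would be invalid or that the trial is underpowered for its primary outcome. The change is worth making because it costs almost nothing, not because a large loss has been shown.

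**What to change.** 1. Reconcile 8.1 with 3.1 and 8.2 on whether pain or overall complication rate is primary, and give the pain endpoint a time window.
2. In 8.3, define one early-pain summary per patient, for example the mean over the Day 0-4 calls, or specify a repeated-measures model over the nine calls. Without this, an adjusted model has no single outcome to act on.
3. Add an analysis with terms for arm and preoperative VAS: ANCOVA with robust or bootstrap standard errors, or a proportional-odds model. Report the arm effect with its 95% CI. Quade's rank ANCOVA can supply an adjusted P value, but it does not by itself give an effect estimate with an interval. The covariate need not share the outcome's scale, so the preoperative VAS can be used with the 1-10 phone score.
4. Show the adjusted result beside the stated Mann-Whitney test and label it as added after data were seen. If it is specified before arm-level pain results are examined, it can be the main pain comparison.

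The cost is a short addition to 8.3 and some analysis syntax, with no new data, visits or patients. The downsides are one degree of freedom, the assumptions of the chosen model, and its post hoc status if it is specified late.

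### The 12-week VAS, SANE, ASES and Penn scores are compared without the preoperative values already collected: the test is valid, but precision goes unused, by an amount the documents do not fix

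*Combined protocol and SAP*

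**What the plan says.** Section 3.1 describes both measurements. Before surgery: "Preoperatively, patient demographics and baseline Visual Analog Scale, Single Assessment Numeric Evaluation, American Shoulder and Elbow Surgeons, and Penn Shoulder Scores were obtained". At follow-up: "At 12 weeks postoperatively, Visual Analog Scale, Single Assessment Numeric Evaluation, American Shoulder and Elbow Surgeons, and Penn scores were reassessed". On the analysis, the same section says "Outcome scores were compared with Mann-Whitney U tests", and section 8.3 says that "preoperative and postoperative PROMs (VAS, SANE, ASES, and PSS) were compared using Mann-Whitney U tests". Neither section names a change score, a covariate or a model for these four scores. ANCOVA and LSMEANS appear in the abbreviation list (9.2), but no analysis uses them.

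On their standing, the synopsis (1.1) has as an objective "Compare patient-reported outcome measures" and lists the four scores at 12 weeks as endpoints. They are not the primary outcome under section 3.1 ("The primary outcome was overall complication rate"). Section 8.1 has "Primary Efficacy Endpoint(s): Postoperative Pain Scores", and its secondary list is "Postoperative Oral Morphine Equivalents, Analgesia Satisfaction, Analgesia Complications, Sleep Quality, and Hours of Painless Sleep". It does not mention SANE, ASES, Penn or a 12-week time point.

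**The concern.** A patient's shoulder score before surgery is likely to carry some information about the score at 12 weeks. If it does, comparing the 12-week scores alone leaves explainable between-patient variation in the noise. The trial collects the baseline of all four instruments and then compares arms at each time point separately, so that information is not used.

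At stake is the precision of the 12-week comparison. The only power statement (8.2) rests on complication rates, so nothing in the documents shows how well the 12-week scores can separate the arms. Section 8.3 also names no effect estimate or interval for them. If the comparison is non-significant, a reader will want to know how large a difference remains possible, and a baseline-adjusted estimate with an interval would help to answer that.

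**Working it through.** **The plan's own figure.** There is none to reproduce. Section 8.2 gives power 0.8 and alpha 0.05 for complication rates, without the rates or the sample size, and gives nothing for the 12-week scores.

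**Inputs.** Alpha 0.05 is from section 8.3; two-sided is assumed. The correlation r, the total sample size N and the starting power are all assumptions, shown as ranges.

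**Step 1: variance.** The ratio of adjusted to unadjusted variance is 1 − r², and the equivalent sample multiplier is 1/(1 − r²).

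| r | 1 − r² | multiplier |
|---|---|---|
| 0.1 | 0.99 | 1.01 |
| 0.3 | 0.91 | 1.10 |
| 0.5 | 0.75 | 1.33 |
| 0.6 | 0.64 | 1.56 |

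**Step 2: break-even.** Estimating one more coefficient multiplies the variance by (N − 3)/(N − 4). Adjustment pays when (1 − r²)(N − 3)/(N − 4) < 1, that is, when r > √(1/(N − 3)).

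- N = 40: √(1/37) = 0.16
- N = 80: √(1/77) = 0.11
- N = 124: √(1/121) = 0.09
- N = 200: √(1/197) = 0.07

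**Step 3: power.** Adjusted power is Φ(c/√(1 − r²) − 1.960), where c = 1.960 + z(starting power).

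- Start 80%: c = 1.960 + 0.842 = 2.802. At r = 0.3, Φ(2.802/0.954 − 1.960) = 83.6%. At r = 0.5, Φ(2.802/0.866 − 1.960) = 89.9%.
- Start 20%: c = 1.960 − 0.842 = 1.118. At r = 0.3, Φ(1.118/0.954 − 1.960) = 21.5%. At r = 0.5, Φ(1.118/0.866 − 1.960) = 25%.

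The relative saving in variance does not depend on the starting power. The gain in percentage points does.

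**Step 4: does an ordinal model deliver this?** Two simulations with an assumed 11-level score:

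- 5,000 runs per cell, 30% of patients at the floor, ranked baseline, 40, 62 or 100 per arm. Mann-Whitney power was 79–81%. The adjusted proportional-odds model gave 80–81% at r = 0.1, 83–84% at r = 0.3 and 88–90% at r = 0.5.
- 1,000 runs per cell, a skewed score, the baseline entered as a standardised score, total N of 60 and 100. Mann-Whitney against the adjusted model gave 0.78 vs 0.83 and 0.75 vs 0.80 at r = 0.3, and 0.74 vs 0.84 and 0.77 vs 0.87 at r = 0.5.

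**Step 5: size under the null.** The first simulation rejected in 4.7–5.7% of runs. The second, using a likelihood-ratio test, rejected in 5.5–6.7% for the adjusted model against 4.4–6.3% for Mann-Whitney (simulation error about 0.7 points). A separate 500-run check of the likelihood-ratio test gave 6.6–8.0%, with error of about √(0.05 × 0.95/500) = 1.0 point. Part of the simulated gain may therefore be excess type I error.

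**Step 6: missing baselines.** With 62 per arm and 20% of baselines missing at random, filling in the mean rank left the ordinal model at 80%, 83% and 86% power at r = 0.1, 0.3 and 0.5. Dropping those patients (simulated with rank ANCOVA) gave 70%, 72% and 79%. At r of 0.3 or less that is worse than not adjusting at all.

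**The case against.** The strongest reply is that this is an analyst's preference. Mann-Whitney is a defensible choice for non-normal scores, and randomization makes it valid without the baseline. That stands. A reader might infer that ignoring the baseline biases the comparison or makes it an error; the documents do not support that.

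Second, no gain can be demonstrated for this trial, because r, N and a target difference are all absent. This also stands. Quoting only the gain from 80% would mislead, since nothing ties the 12-week scores to 80% power; from 20% the gain at r = 0.3 is 1.5 points. A reader might also take r = 0.3 as the point where adjustment starts to pay. It is not: break-even is near 0.1, and at 0.3 the gain is still modest.

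Third, the opportunity may have passed. Section 8.3 is in the past tense and reports a Shapiro-Wilk result, the synopsis title states findings, and two references were accessed in March 2022, after the study end date of December 1, 2021. This does not prove that the 12-week scores had been compared, but it decides how an added model must be labelled.

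Fourth, the model brings its own weaknesses: a proportional-odds assumption, four more P-values, and slight over-rejection in small samples. These are reasons to keep it supportive, not to omit it. It also does nothing for missing 12-week scores, which affect either analysis.

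Finally, the absence of estimates and intervals in section 8.3 is not specific to these scores, and the section does not say that only P-values will be reported. It should not add weight here.

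**Conclusion.** The point holds as a modest, optional improvement. Four preoperative scores are collected and not used when the same scores are compared at 12 weeks. The planned test is valid, and nothing in the documents shows that its conclusion would change.

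The size is conditional on r: variance falls by about 9% at r = 0.3 and 25% at r = 0.5, with almost no gain at r = 0.1. Break-even runs from about 0.07 at a total N of 200 to 0.16 at 40. In power this could be 4 to 10 points if the comparison starts near 80%, or 1.5 to 5 points if it starts near 20%. The variance and power figures use the standard normal-theory approximation; the simulations agree in direction but assume a score shape that the documents do not give.

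The priority is low because these scores are not listed in section 8.1. That section gives its pain scores no time point, so a reader might infer that the 12-week VAS is covered. The synopsis, however, separates pain on days 0 to 4 from the 12-week measures, and section 8.1 says nothing about 12 weeks.

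**What to change.** Add to section 8.3:

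> Each 12-week score (VAS, SANE, ASES, PSS) is also compared between arms by a proportional-odds model with arm and the rank of the preoperative value of the same score as covariates. The odds ratio, conditional on baseline, is reported with its 95% confidence interval. A patient with a missing preoperative score is kept, with the rank set to the mean rank over both arms. The Mann-Whitney test remains the planned comparison and is reported beside the model. The model is supportive, and its P-value does not override the Mann-Whitney result.

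If the data have already been examined, label the model post hoc as well. The VAS line applies only if VAS is collected at 12 weeks: the synopsis and section 3.1 say so, but section 3.2 leaves VAS out of its 12-week list, so these sections should be reconciled.

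The cost is one paragraph and four model fits, with no new patients or data. Each model uses one degree of freedom for the baseline and rests on proportional odds; the Mann-Whitney result beside it does not need that assumption. The odds ratio is not on the same scale as an unadjusted one: in simulation, the same shift between arms gave about 0.39 at r = 0.1 and 0.30 at r = 0.6. It should be described as conditional on baseline wherever it is reported.
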